#### *2.4.4.1.2 Proportion of Relapse free patients*

The proportion of patients with relapse-free each year from prior studies (CAMMS323/324) until the end of TOPAZ study will be estimated based on Kaplan-Meier methods. The complementary log-log transformation will be used to construct 95% confidence intervals. A Kaplan-Meier graph summarizing the event probability over time will be presented by subgroups (IAT vs DAT) and by alemtuzumab courses. Hazard ratio and corresponding 95% confidence interval will be calculated using Cox proportional hazards (PH) regression with robust variance estimation (6). Covariates for the Cox PH model will include analysis groups and geographic region and prior clinical studies. Inference will be based on the Wald test of the log hazard ratio (estimated regression coefficient from the model). The analysis period starts from prior studies (CAMMS323/324) until the end of TOPAZ study.

The Kaplan-Meier (KM) estimates will be summarized for retreated population separately.

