### ***Disease characteristics at baseline***

Specific disease history includes

- Baseline EDSS (TOPAZ baseline and long-term baseline)
- Time (years) since initial/last clinical episode
- Brain imaging characteristics (e.g. Gadolinium-Enhancing lesion count, T1-Hyperintense Lesion Volumes and T2-Hyperintense Lesion Volumes) (TOPAZ baseline and long-term baseline)

Any technical details related to computation, dates, and imputation for missing dates are described in [Section 2.5](#).

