##### **2.4.4.1 Analysis of efficacy endpoint(s)**

###### **2.4.4.1.1 Annualized relapse rate (ARR)**

The estimated annualized relapse rate using negative binomial model with robust variance estimation will be presented by year and in overall. The observed total number of relapses is the dependent variable, the log total amount of follow-up time in years for each patient will be the offset variable and analysis group indicator (IAT vs DAT) and geographic region will be the covariates in the model. Both IAT vs DAT comparison and ARR by alemtuzumab courses will be analyzed. The analysis period starts from prior studies (CAMMS323/324) until the end of TOPAZ study. The model will also be stratified by previous clinical study.

The observed annualized relapse rate will be reported as well, which is defined as the total number of relapses divided by the total years of follow-up for each patient.

The ARR will be presented separately for retreated population in overall group.

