#### *2.4.4.1.3 EDSS*

The observed value, change from baseline as well as percentage change from baseline will be presented descriptively. The change from baseline in EDSS will be analyzed using a mixed model for repeated measures (MMRM) (7)(8)(9) with baseline EDSS score, analysis group indicator (IAT and DAT), geographic region, study visit and study visit by analysis group interaction as covariates. The TOPAZ study baseline at study entry is considered as post-baseline for efficacy analysis. The comparison of the change from baseline in EDSS with the MMRM will include the change from baseline to each consecutive year which can be constructed using the linear contrasts of the estimated regression parameters. All post-baseline EDSS scores will be included in the MMRM; patients without any post-baseline scores will not be included. For this model, imputation will not be used.

Similar analysis for change of EDSS by alemtuzumab courses and for retreated population will be analyzed as well.

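### The IAT vs DAT relapse models contain no baseline disease covariate, although long-term baseline EDSS and Gd-enhancing lesion count are available; adding them is a small, nearly free gain and a partial guard against selection

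*SAP*

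**What the plan says.** SAP 2.4.4 names IAT versus DAT as the main long-term efficacy comparison. Two relapse models serve it.

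- **Relapse rate (SAP 2.4.4.1.1).** A negative binomial model with robust variance and a log follow-up offset: "analysis group indicator (IAT vs DAT) and geographic region will be the covariates in the model". It adds: "The model will also be stratified by previous clinical study".
- **Relapse-free proportion (SAP 2.4.4.1.2).** A Cox model with robust variance: "Covariates for the Cox PH model will include analysis groups and geographic region and prior clinical studies". It continues: "Inference will be based on the Wald test of the log hazard ratio".

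The other efficacy models do adjust for baseline. The EDSS repeated-measures model is fitted "with baseline EDSS score, analysis group indicator (IAT and DAT), geographic region, study visit and study visit by analysis group interaction as covariates" (SAP 2.4.4.1.3). The lesion-count models use the long-term baseline count (SAP 2.4.4.1.4), and the lesion-volume model uses baseline volume (SAP 2.4.4.1.5).

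SAP 2.1.1 defines the long-term baseline for EDSS and MRI as the final value before the first alemtuzumab or interferon dose in the parent study. Its disease-characteristics list includes "Baseline EDSS (TOPAZ baseline and long-term baseline" and, for imaging at the same two baselines, "Gadolinium-Enhancing lesion count, T1-Hyperintense Lesion Volumes and T2-Hyperintense Lesion Volumes". Relapse history appears only as "Time (years) since initial/last clinical episode"; no pre-study relapse count is listed. SAP 2.4.1 tabulates these variables by IAT and DAT.

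**The concern.** Relapse counts vary widely between patients. A baseline variable that predicts relapse absorbs part of that variation and protects the comparison if the groups differ on it. The relapse models use none, although suitable candidates are already defined.

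Balance cannot be taken for granted. The parent studies were randomized (Protocol Section 4), but the analysed groups are what remains after several later steps. Patients must have completed at least 48 months of CAMMS03409 (Protocol 7.1) and chosen to join (SAP 1.3). DAT patients must also have gone on to alemtuzumab in the extension, whereas IAT patients needed only alemtuzumab in the parent study (SAP 2.3.3). A filter that differs by arm can leave the arms with different baseline prognosis, and an unadjusted rate ratio or hazard ratio passes that difference on to the reader.

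**Working it through.** The documents give no sample size, power, event count or effect size for this comparison, so there is no plan figure to reproduce. The size of the effect was examined under assumptions.

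**Assumed inputs (none from the documents).** 800 patients, 67% IAT, 11 years of follow-up, DAT relapse rate 0.2 per year, true rate ratio 0.70, gamma frailty variance 0.8, and one standardized baseline covariate with effect b on the log rate per SD. There were 40 simulated data sets per setting. Each was analysed with and without the covariate. Region, study strata and robust variance were left out.

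**1. Precision, no imbalance.**

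| b | NB SE without → with | Ratio | Cox SE without → with | Cox HR without → with | Cox mean z without → with |
|---|---|---|---|---|---|
| 0.15 | 0.0875 → 0.0868 | 0.992 | 0.0912 → 0.0913 | 0.764 → 0.762 | -2.95 → -2.98 |
| 0.30 | 0.0903 → 0.0875 | 0.969 | 0.0918 → 0.0920 | 0.787 → 0.785 | -2.61 → -2.64 |
| 0.50 | 0.0961 → 0.0888 | 0.924 | 0.0934 → 0.0935 | 0.810 → 0.802 | -2.26 → -2.36 |

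The rate-ratio standard error falls by about 1%, 3% and 8%. The Cox standard error does not fall. Omitting a prognostic covariate from a Cox model instead pulls the hazard ratio towards 1. Adjustment moves it back by 0.002 to 0.008 here, and mean z rises by about 1% (2.98/2.95) to 4% (2.36/2.26). With 40 runs, hazard-ratio shifts this small show direction rather than exact size.

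**2. Analytic cross-check for the rate model.** Per-patient variance of the log rate is 1/μ + k, with μ = 11 × ARR. Replace k by k(1 − R²) when the baselines explain a share R² of between-patient variance.

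- ARR 0.15 (μ = 1.65), k = 0.5, R² = 10%: 0.606 + 0.500 = 1.106 becomes 0.606 + 0.450 = 1.056. SE ratio √(1.056/1.106) = 0.977.
- ARR 0.20 (μ = 2.20), k = 1.5, R² = 20%: 0.455 + 1.500 = 1.955 becomes 0.455 + 1.200 = 1.655. SE ratio √(1.655/1.955) = 0.920.

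That is a gain of 2% to 8%, in line with step 1.

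**3. What this does to an interval.** At b = 0.30 and a rate ratio of 0.70, exp(1.96 × 0.0903) = 1.194 gives 0.586 to 0.836. With the covariate, exp(1.96 × 0.0875) = 1.187 gives 0.590 to 0.831.

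**4. Bias if the groups differ.** The factor on the rate ratio is exp(b × difference in SD). With b = 0.3 (exp(0.3) = 1.35 per SD):

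- 0.1 SD: exp(0.03) = 1.030
- 0.2 SD: exp(0.06) = 1.062

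On the log scale these are 0.03/0.0903 = 0.33 and 0.06/0.0903 = 0.66 of a standard error. Over b = 0.15 to 0.5 the factor runs from 1.015 (0.15, 0.1 SD) to 1.105 (0.5, 0.2 SD). The simulation at 0.1 SD and b = 0.3 gave 0.732 unadjusted and 0.707 adjusted (truth 0.70). The Cox hazard ratio was 0.794 unadjusted and 0.772 adjusted.

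**5. How large is chance imbalance?** Its SD is √(1/n₁ + 1/n₂). For 400 and 400 this is 0.071; for 536 and 264 it is 0.075. Thus 0.1 SD is about 1.3 to 1.4 chance SDs, and 0.2 SD is about 2.7 to 2.8.

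**The case against.** The case for leaving the models alone has real force.

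- **The method is valid and follows the protocol.** Protocol 11.4.1 asks for a negative binomial model with robust variance stratified by study. The SAP does that and adds region. Efficacy is secondary, and Protocol 11.4 plans no formal tests. This stands: the point is an improvement, not the correction of an invalid analysis.
- **No imbalance is shown.** A reader might infer that IAT and DAT differ at baseline. The documents report no baseline data by group, and the planned tables would reveal a difference in these variables. This stands. But if the covariates are chosen only after those tables are seen, the choice is post hoc.
- **Not both intervals are too wide.** A reader might infer that the hazard ratio also loses precision. Step 1 shows that it does not.
- **The SAP is not inconsistent.** The EDSS and MRI models adjust each outcome for its own baseline. The matching covariate for relapse is the pre-study relapse count, which the SAP does not list. The different treatment of relapse is therefore not an error in itself.
- **Predictive strength is assumed.** The documents do not say how well EDSS or Gd-lesion count predicts relapse, or how complete the baseline values are. Imbalances beyond 0.2 SD would imply larger bias, but nothing in the documents points to differences of that size.

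What survives is that the selection steps differ by arm, the variables are already defined, and the adjustment costs almost nothing. SAP 2.4.4 says the groups will be compared, so the ratios will be read as between-group effects even without formal testing.

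**Conclusion.** The point holds in modest form. Both IAT vs DAT relapse models omit available baseline disease covariates. Adding them would cut the standard error of the rate ratio by about 1% to 8% and slightly reduce attenuation of the hazard ratio, with a small gain in power. If selection into TOPAZ has left a 0.1 to 0.2 SD difference in a baseline worth 1.35 per SD, the unadjusted rate ratio is off by about 3% to 6%. All these sizes rest on assumed follow-up, relapse rate, dispersion and covariate strength.

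A reader might infer that baseline adjustment would make the comparison unconfounded, or would also rescue the analysis by number of courses. Neither follows. Selection happened after randomization, and parent-study baselines capture only part of it. In CAMMS03409, extra courses were offered on evidence of renewed disease activity (Protocol Section 4), and in TOPAZ they are at the investigator's discretion (Protocol 6.1). Course count therefore partly reflects the relapse outcome itself.

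**What to change.** Before database lock, amend SAP 2.4.4.1.1 and 2.4.4.1.2 so that the IAT vs DAT models also include long-term baseline EDSS and long-term baseline Gd-enhancing lesion count, plus pre-study relapse count if it is held from the parent studies. Keep region and prior study. State the form of each term in advance (for example, Gd lesions as present or absent) and give a simple rule for missing baselines, such as single imputation made without regard to group, so that no patient drops out of the model. If the sponsor prefers to keep the present models as the main ones, prespecify the adjusted versions as sensitivity analyses.

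Do not present this as a remedy for the by-course analysis, and say in the report that adjustment reduces selection bias without removing it.

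The cost is a line or two in each section, with no new data collection. There are two minor downsides: some missing values need handling, and the hazard ratio becomes conditional on baseline, so it is not directly comparable with an unadjusted one.

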## 6 STUDY DESIGN

### 6.1 DESCRIPTION OF THE PROTOCOL

This study is a Phase 3B/4, international, multicenter, open-label, non-comparative study to evaluate the long-term safety, efficacy and QoL of alemtuzumab in patients who have completed at least 48 months of the extension study CAMMS03409. In addition, impact of treatment on pharmaco-economic data will be evaluated.

Patients treated with alemtuzumab within 48 months prior to enrollment in the LPS13649 study must be followed-up at monthly intervals until 48 months after the last infusion of alemtuzumab ([Section 10.1.6.2](#)).

Scheduled visits for safety and efficacy assessments will be performed every six months. AEs and concomitant medications will be monitored continuously. Quality of life, pharmaco-economic data and brain imaging will be collected every twelve months.

Patients must contact the treating neurologist at the study site (Study Investigator) as soon as they experience any sign or symptom of MS relapse. The Study Investigator will decide on the need to schedule extra visits (unscheduled visits) to evaluate the patient's status. All procedures and assessments will be collected in the e-CRF.

At the Study Investigator discretion patients can be treated:

- Patients may receive additional courses of alemtuzumab but not sooner than 12 months from any previous alemtuzumab treatment course, or
- Patients may receive other commercial DMTs.

In the event that a Study Investigator decides to treat a patient (with alemtuzumab or another DMT) the factors contributing to the decision to treat (eg, patient is experiencing clinical and/or imaging activity) should be documented in the e-CRF.

For treatment courses of alemtuzumab the Study Investigator should refer to the safety information in the Investigator's Brochure (IB) or in the approved label in the country/region when available. All treatment courses will consist of 12 mg/day alemtuzumab intravenously infused once daily on 3 days ([Section 8.1](#)).

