### **11.4 STATISTICAL METHODS**

All data collected in this study will be reported using summary tables, figures, and patient data listings. Summary statistics will be computed and displayed by treatment group (assigned in the original study) and scheduled assessment time. Summary statistics for continuous variables will minimally include n, mean, standard deviation, minimum, median, and maximum. For categorical variables, frequencies and percentages will be presented. Graphical displays will be provided as appropriate. No formal inferential hypothesis tests will be performed, however 2-sided 95% confidence intervals (CI) will be provided where appropriate.

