#### **11.5 INTERIM ANALYSIS**

No interim analysis is planned; an annual partial database lock will be made available for publication purpose.

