#### **2.4.4 Analyses of efficacy endpoints**

The efficacy population will be used for all efficacy analyses.

For MRI endpoints, EDSS, questionnaires endpoints, only data collected in TOPAZ study will be used for analysis in addition of baseline information from previous studies. The long-term baseline is defined as the last available assessment prior to first dose of alemtuzumab or SC IFNB-1a administration in prior studies. It will be applied to long-term efficacy analysis.

For relapse endpoints, data from prior studies (CAMMS323, CAMMS324 and CAMMS03409) should be obtained.

The main long-term analysis for efficacy endpoints is IAT versus DAT comparison. The efficacy of immediate alemtuzumab treatment (Subgroup IAT defined in [Section 2.3.3](#)) and delayed alemtuzumab treatment (Subgroup DAT defined in [Section 2.3.3](#)) groups will be compared for relapse related endpoints, EDSS assessment as well as MRI endpoints.

The analysis in reference of long-term baseline in prior studies by total number of alemtuzumab courses (i.e.  $\leq 3$  vs  $> 3$ ) will be summarized as well.

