### 3 INTERIM ANALYSIS

A yearly interim analysis is planned for this study. Only data collected in TOPAZ study will be used for this interim analysis. Generally, demographic and disposition of patients, summary of safety results, and summary of efficacy results will be provided.

For safety, key safety results including TEAE, SAE, AESI, death, AEs leading to treatment discontinuation along with related laboratory values and vital sign values in which details are provided in [Section 2.4.5](#) will be provided in the interim analysis report. For efficacy, the interim analysis is performed for EDSS, relapse and MRI related efficacy endpoints and Quality of life outcomes in which details are provided in [Section 2.4.4](#). Summary of demographics and disposition of patients will also be provided.

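### The SAP plans a Wald test and yearly interim efficacy analyses that the protocol does not allow, records no modification, and leaves the IAT vs DAT results without a descriptive, unadjusted label

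*SAP*

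**What the plan says.** **Protocol.** Section 6.1 sets the design: "This study is a Phase 3B/4, international, multicenter, open-label, non-comparative study to evaluate the long-term safety, efficacy and QoL of alemtuzumab". Section 11.4 sets the rule on testing: "No formal inferential hypothesis tests will be performed, however 2-sided 95% confidence intervals (CI) will be provided where appropriate". The same section plans the display by group: "Summary statistics will be computed and displayed by treatment group (assigned in the original study) and scheduled assessment time". Section 11.4.1 adds a negative binomial model with robust variance for the relapse rate, stratified by study, and leaves the detailed efficacy methods to the SAP. On interim looks, Section 11.5 (and 6.3 in the same words) says: "No interim analysis is planned; an annual partial database lock will be made available for publication purpose".

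**SAP.** Section 1.1 repeats the non-comparative label. Section 2.4.4 then says: "The main long-term analysis for efficacy endpoints is IAT versus DAT comparison". For the proportion relapse free, Section 2.4.4.1.2 gives a Cox hazard ratio with a 95% confidence interval and adds: "Inference will be based on the Wald test of the log hazard ratio". Sections 2.4.4.1.3 to 2.4.4.1.5 describe further IAT vs DAT comparisons: yearly MMRM contrasts for EDSS, negative binomial and GEE models for lesions, and a yearly ranked ANCOVA for lesion volume. Section 3 opens: "A yearly interim analysis is planned for this study". It covers EDSS, relapse, MRI and quality of life, and refers to Section 2.4.4 for details. Sections 1.5, 1.6 and 2.4.4.2 (modifications to the protocol's statistics, modifications within the SAP, multiplicity) are each marked not applicable.

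**The concern.** A plan without tests can reasonably treat multiplicity as not applicable. A plan that names a test, makes a group comparison its main efficacy analysis and repeats efficacy every year cannot do so without saying how the results are to be read. The SAP's efficacy sections give no alpha, no hierarchy and no statement that results are nominal or exploratory.

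What is at stake is the status of the efficacy claims. The patients are elective participants who completed at least 48 months of the extension study, and no sample size calculation supports a comparison (Protocol 7.1, 11.1). An unlabelled p-value for IAT vs DAT could be taken as randomised, confirmatory evidence. The annual lock exists for publication, so such a result could appear in print before the final analysis. Because SAP 1.5 declares no departure, a reader of the study report would not learn that the protocol had excluded the test.

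**Working it through.** **1. Testing.** Protocol 11.4.1 delegates detailed methods to the SAP, but 11.4 fixes the no-test rule for all data. Delegating the method does not lift that rule. The Cox model in SAP 2.4.4.1.2 already yields the hazard ratio and its 95% interval, both of which the protocol allows. The Wald sentence therefore adds only the part that the protocol excludes.

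**2. Interim analysis.** An outdated protocol version does not explain the mismatch. According to Protocol Appendix E, the amendment of 27-Feb-2018 replaced an interim analysis with the annual partial lock. The SAP carries the list of adverse events of special interest that came in with amended protocol 03 (28-Jan-2020). It therefore follows the later protocol elsewhere.

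**3. Whether SAP 3 can be carried out.** Section 3 restricts interim analyses to TOPAZ data and refers to Section 2.4.4 for the methods. The relapse models in 2.4.4.1.1 and 2.4.4.1.2 start in CAMMS323/324. The interim relapse analyses cannot satisfy both.

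**4. Size (illustration).** The documents give no alpha, power or event count for these comparisons, so there is no figure to reproduce.

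- Endpoints counted from SAP 2.1.3: ARR, relapse free, EDSS, Gd-enhancing, new Gd-enhancing, new/enlarging T2, new T1, new hypointense T1, T1 volume, T2 volume, BPF. This gives k = 11.
- Assumptions: each comparison is read once, at the final analysis, at two-sided 0.05 (the level implied by a 95% interval), and there is no true difference on any endpoint.
- If independent: P(at least one) = 1 − 0.95^k = 1 − 0.95^11 = 1 − 0.569 = 0.431.
- If equally correlated (simulated normal statistics, 400,000 replicates, |Z| > 1.96):

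| Assumed correlation | Chance of at least one nominal difference, k = 11 |
|---|---|
| 0 | 43% |
| 0.3 | 37% |
| 0.5 | 30% |
| 0.8 | 18% |

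- Sensitivity to the count, independent case: SAP 2.4.4.1.5 names only lesion volume for the between-group ANCOVA. Without BPF the value is 1 − 0.95^10 = 0.401. Without the two relapse endpoints but with BPF it is 1 − 0.95^9 = 0.370.
- Repetition: one endpoint read at 0.05 at five equally spaced cumulative looks gives about 14% instead of 5% (simulated). Five looks is an assumption based on the 5-year duration.

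Yearly contrasts, the analyses by number of courses (≤3 vs >3) and the retreated-population analyses are not counted and would raise these figures.

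**5. Where the illustration does not apply.** The ARR and Cox analyses include the period when the DAT group received SC IFNB-1a. Protocol Section 4 says that superiority over interferon was already established in the earlier studies. No true difference is not a realistic null for these endpoints, so the 18–43% range does not describe the Wald test itself. Endpoints measured as change from the long-term baseline share this limit in part.

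**The case against.** **Comparison is within the protocol.** Protocol 11.4 plans display by originally assigned group with confidence intervals, and 11.4.1 prescribes a model. A reader might infer from the non-comparative label that any IAT vs DAT contrast is forbidden. The documents do not support that. Modelled estimates with intervals are compatible, and only the Wald sentence is named as inference. This part of the objection stands.

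**Chance findings are not near certain.** A reader might multiply endpoints by years, assume independence and conclude that some significant result is almost guaranteed. The documents give no such count, yearly changes share patients and a baseline, and cumulative lesion counts are nested. Correlation lowers the figure substantially. This also stands.

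**No confirmatory alpha is being spent.** The study is open-label, efficacy is secondary, there is no stopping rule, and SAP 2.4.5 keeps safety descriptive without systematic testing. The route to annual publication comes from the protocol's own lock, not from the SAP. All this is true, and it confines the point to how efficacy results are reported. It does not remove the two contradictions or explain why SAP 1.5 records neither.

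**Intervals carry the same signal as p-values.** Replacing a p-value with an unadjusted 95% interval leaves the chance of a nominal difference unchanged. Correct: the gain is in how the result may be interpreted, so the label has to be explicit.

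**Conclusion.** The point holds as a conflict between SAP and protocol on two matters, formal inference and interim analysis, compounded by SAP 1.5 and 2.4.4.2. IAT vs DAT estimation is not itself in conflict. The consequence is limited to secondary efficacy claims; the primary safety analysis is unaffected.

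The 18–43% figure is an illustration. It rests on 11 endpoints, a 0.05 reading of each, a global null and assumed correlations from 0.8 down to 0. It excludes yearly contrasts, which would raise it, and it is not an estimate for the relapse endpoints. A reader might also infer that IAT vs DAT results should be withheld until the final lock. The protocol gives no basis for that, since it allows display by original group and an annual lock for publication. The SAP should be reconciled with the protocol before further efficacy results are reported.

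**What to change.** - **SAP 2.4.4.** Delete the Wald-inference sentence. State that all IAT vs DAT results are estimates with two-sided 95% confidence intervals, descriptive and not adjusted for multiplicity, and that an interval excluding the null is not to be reported as a confirmatory finding. Put the same statement in 2.4.4.2.
- **SAP 3.** Rewrite it as the protocol's annual partial database lock with descriptive summaries. Reconcile the TOPAZ-only restriction with the relapse models that start in CAMMS323/324, for example by saying which relapse summaries are produced from TOPAZ data alone.
- **If a formal test or an interim analysis is wanted.** Amend Protocol 11.4, or 6.3 and 11.5, name one endpoint and one time point, and record the change in SAP 1.5.

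The first two changes cost SAP wording only. They need no new data and remove no planned model or estimate; the sponsor gives up only a test that the protocol does not provide for. The third would need a protocol amendment.
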